18.7 Efficacy

18.7.1 Efficacy Assessments

The primary efficacy endpoint of the study is the percentage of subjects with clinical cure (complete resolution of signs and symptoms) at the TOC visit. Secondary efficacy endpoints include the percentage of subjects with mycological eradication (negative fungal culture) at the TOC visit, the percentage of subjects with both clinical cure and mycological eradication at the TOC and FU visits, the percentage of subjects with continued clinical

response (continued absence of signs and symptoms) at the FU visit and the time to resolution of signs and symptoms after initiation of study drug. The percentage of subjects with a negative KOH test at the TOC visit, the percentage of subjects who are free of signs and symptoms at the FU visit, the percentage of subjects by *Candida* species infection at Baseline, the percentage of isolates susceptible to SCY-078 and fluconazole, the percentage of subjects with clinical cure (complete resolution of signs and symptoms) at TOC by *Candida* species and the percentage of subjects with mycological eradication (negative fungal culture) at TOC by *Candida* species will be evaluated as exploratory endpoints.

The following treatment outcome definitions will be used for the assessment of efficacy:

Clinical Outcome

- **Clinical cure:** Complete resolution of signs and symptoms of vulvovaginal infection without need for further antifungal treatment. Specifically, for complete resolution, any sign or symptom should be absent (score = 0) by the TOC visit.
- **Clinical failure:** No response to therapy or incomplete resolution of signs and symptoms or need for additional vulvovaginal or systemic antifungal therapy. If the subject receives or self-administers topical drug therapy for the treatment of vulvovaginal irritation/pruritus such as topical analgesic or corticosteroid after completing treatment with the study drug and before the TOC visit, the subject is considered a clinical failure.
- **Continued Clinical Response:** Continued absence of signs and symptoms of vulvovaginal infection at the FU visit in subjects who achieved clinical cure at the TOC visit.
- **Free of Signs and Symptoms:** Absence of signs and symptoms of vulvovaginal infection at the FU visit.
- **Mycological Outcome**
- **Mycological eradication:** A subject with negative culture (no growth) for *Candida* species.
- **Mycological persistence:** A subject with a positive culture for *Candida* species.

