8. HANDLING OF MISSING DATA

For the analyses of efficacy endpoints, subjects who have a missing value at the TOC visit or FU visit will be assigned as treatment failures, i.e., non-responders or positive mycological outcome.

The handling of below level of quantitation (BLQ) values in PK analysis will be described in the section below.

No other imputation will be used unless otherwise specified.

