10. DATA CONVENTIONS FOR ANALYSIS

10.1 General Statistical Principles

All statistical tests will be performed at the unadjusted 0.05 (two-sided) or equivalently 0.025 (one-sided) level of significance. The study is not powered for formal statistical comparisons.

All observed and derived variables (e.g., change from baseline, response status) used in the summaries of analyses will be presented in by-subject listings. Descriptive statistics will be used to provide an overview of the efficacy and safety results. For categorical parameters, the number and percentage of subjects in each category will be presented. The denominator for percentage will be based on the number of subjects appropriate for the purpose of analysis. For continuous parameters, descriptive statistics will include number of subjects, mean, standard deviation (SD), median, minimum, and maximum.

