11.8.2 Secondary Efficacy Endpoints

The secondary efficacy endpoints include the following:

- The percentage of subjects with Mycological Eradication (negative fungal culture) at the TOC and FU visit.

Mycological Eradication is defined as a subject with negative culture (no growth) for *Candida* species. Conversely, Mycological Persistence is defined as a subject with positive culture for *Candida* species.

- The percentage of subjects with both Clinical Cure and Mycological Eradication at the TOC visit. If either component assessment is missing, the subject will be considered as missing for this endpoint and imputed as non-responders in the analysis
- The percentage of subjects with both absence of signs and symptoms and Mycological Eradication at the FU visit. If either component assessment is missing, the subject will be considered as missing for this endpoint and imputed as non-responders in the analysis
- The percentage of subjects with Continued Clinical Response at the Follow-up (FU) visit, defined as continued absence of signs and symptoms in subjects who achieved Clinical Cure at the TOC visit
- The time to resolution of signs and symptoms after initiation of study drug, defined as time (days) from first dose of study medication to the first resolution of signs and symptoms. Subjects who discontinued early will be censored at the last available assessment.

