11.8.3 Exploratory Efficacy Endpoints

The exploratory efficacy endpoints include the following:

- Percentage of subjects with a negative KOH test at the TOC visit
- Percentage of subjects who are free of signs and symptoms at the FU visit
- Percentage of subjects by *Candida* species infection at Baseline
- Percentage of isolates susceptible to SCY-078 and fluconazole at the TOC and FU visits
- Percentage of subjects with clinical cure at TOC by *Candida* species at Baseline
- Percentage of subjects with mycological eradication at TOC by *Candida* species at Baseline

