11.9.2 Secondary Efficacy Analyses

The secondary efficacy analyses will be conducted using the mITT, ITT and PP populations.

Binary efficacy endpoints (mycological eradication, composite clinical cure and mycological eradication, and continued clinical response at FU) will be analyzed using the same methods/tests as described for the primary efficacy endpoint.

Time to resolution of signs and symptoms after initiation of study drug will be analyzed using Kaplan-Meier methods. Pairwise treatment comparisons of SCY-078 vs. fluconazole will be performed using log-rank test.

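### The denominator for Continued Clinical Response is not fixed: the wording allows division by TOC cures only, which would test post-randomisation subsets and can reverse the ranking of regimens

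*SAP*

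**What the plan says.** SAP 11.8.2 gives the endpoint as a percentage of subjects with Continued Clinical Response at FU, "defined as continued absence of signs and symptoms in subjects who achieved Clinical Cure at the TOC visit". Protocol 18.7.1 defines it as "Continued absence of signs and symptoms of vulvovaginal infection at the FU visit in subjects who achieved clinical cure at the TOC visit".

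On the denominator, SAP 10.1 offers only a general rule: "The denominator for percentage will be based on the number of subjects appropriate for the purpose of analysis". SAP 11.8.2 adds an explicit non-responder rule to each of the two clinical-plus-mycological composites, but none to this endpoint.

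On the analysis, SAP 11.9.2 says that binary secondary endpoints, this one included, "will be analyzed using the same methods/tests as described for the primary efficacy endpoint". Under SAP 11.9.1 that means a CMH row mean scores test stratified by site, pairwise Fisher tests against fluconazole, and confidence intervals for odds ratios. For populations, "The secondary efficacy analyses will be conducted using the mITT, ITT and PP populations". SAP 8 adds that "subjects who have a missing value at the TOC visit or FU visit will be assigned as treatment failures".

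**The concern.** Cure at TOC is an outcome of treatment, so the subjects cured in each arm are not a randomised comparison. If they form the denominator, a regimen that also cures harder cases may show a lower maintenance rate because those cases could relapse more often, even if treatment does not affect relapse itself. The regimen that leaves more women well at FU could then look worse.

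The primary objective is to choose a regimen. A durability result whose direction depends on an unstated denominator is therefore a poor guide. If the choice is left until after unblinding, it can also be influenced by the data.

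**Working it through.** **Reproducing the plan's figures.** There is nothing to reproduce for this endpoint. The documents state no power, effect size, clinical cure rate by arm or relapse rate. The only design arithmetic, 6 × 30 = 180, agrees. Protocol 7.1 gives 55% for fluconazole, but that is therapeutic cure, which also needs negative KOH and culture, so it is not used here as a clinical cure rate.

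**Which reading does the text support?**

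- *Cured-only denominator.* The phrase "in subjects who achieved clinical cure at the TOC visit" is ordinary wording for a restricted denominator. Protocol 7.2 describes only the exploratory FU endpoint as applying whatever the TOC outcome. Nothing says that a TOC non-cure is a non-responder here.
- *Full denominator.* SAP 11.9.2 runs the endpoint in mITT, ITT and PP. SAP 7 defines no TOC-cured population. SAP 8 makes a missing TOC or FU value a failure.

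Both readings are open. SAP 8 does not settle it, because its effect depends on the choice. With a missing TOC value imputed as failure, the subject is not a TOC cure: she leaves a cured-only denominator but counts as a non-responder in a full one.

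**When do the two denominators disagree?** Let c be the proportion cured at TOC and r the proportion of those still clear at FU. The cured-only rate is r and the all-subject rate is c × r. If arm A has the higher cure rate, it leads over all subjects but trails among the cured when

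1 < r_B / r_A < c_A / c_B.

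**Hypothetical counts, 30 per arm.**

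| | Cured at TOC | Clear at FU | Among cured | Over all |
|---|---|---|---|---|
| A | 24 | 18 | 18/24 = 75.0% | 18/30 = 60.0% |
| B | 15 | 13 | 13/15 = 86.7% | 13/30 = 43.3% |

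Here r_B/r_A = 0.867/0.750 = 1.16 and c_A/c_B = 0.80/0.50 = 1.60, so the order flips. The odds ratio for A v B is (18 × 2)/(6 × 13) = 0.46 among the cured (Fisher p = 0.45) and (18 × 17)/(12 × 13) = 1.96 over all subjects (p = 0.30). Neither is significant; it is the direction that changes.

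**Can it happen with no treatment effect on relapse?** Assume half the subjects are easy (90% cured in both arms, 90% of those stay clear) and half hard (60% cured in A, 20% in B, 60% of those stay clear).

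- A: cured 0.5 × 0.9 + 0.5 × 0.6 = 0.75; cured and still clear 0.5 × 0.9 × 0.9 + 0.5 × 0.6 × 0.6 = 0.585; ratio 78.0%.
- B: cured 0.5 × 0.9 + 0.5 × 0.2 = 0.55; cured and still clear 0.405 + 0.06 = 0.465; ratio 84.5%.

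The expected rates are A 78.0% v B 84.5% among the cured, but A 58.5% v B 46.5% over all subjects. In 400,000 simulated pairs of arms, B led among the cured while A led overall in 41%, 46% and 50% of draws at 20, 25 and 30 per arm (the mITT size is unknown, so a range is used). With a milder contrast (hard cases cured in 60% v 40%) the range was 22% to 27%.

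Part of this is sampling noise. With the same 80% maintenance among the cured in both arms, and cure of 70% v 55%, the same disagreement occurred in 32% of draws at 30 per arm. The expected rates, not the frequencies, show the selection effect.

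**The case against.** A reader might infer that the plan does compare arms on post-randomisation responders. The documents do not support that. They state no denominator, they name only mITT, ITT and PP for this endpoint, and the failure rule in SAP 8 fits a full denominator at least as well. The remark in Protocol 7.2 may distinguish who counts as a responder, not who is counted. This part of the objection stands, and the finding is limited to an unspecified denominator.

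It can also be said that the plan already has two FU measures not conditioned on TOC cure: the secondary composite of absent signs and symptoms with mycological eradication (SAP 11.8.2), and the exploratory "Percentage of subjects who are free of signs and symptoms at the FU visit". Both exist and would temper a misleading conditional rate. Neither replaces this endpoint. The composite also needs a negative culture, the exploratory measure is not run in ITT (SAP 11.9.3), and neither requires cure at TOC, so neither measures sustained clinical cure.

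Finally, the cure and relapse rates above were chosen to show a reversal, and higher cure rates would narrow the gap between the denominators. That is correct; the figures show that a reversal is possible, not that it is likely in this trial. Maintenance among cured subjects is also a reasonable description of durability, and the fix keeps it in that role.

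**Conclusion.** The point holds as a gap in specification that matters for interpretation. A permitted literal execution of the SAP would put p-values on non-randomised subsets, drop subjects with missing TOC, and could reverse the order of two regimens (75% v 87% against 60% v 43% in the hypothetical counts). The other permitted execution avoids all three.

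The reach is limited. The primary endpoint is unaffected, the study is exploratory and not powered for formal comparisons, and no section makes the dose choice depend on this endpoint. It would go too far to conclude that the trial will misrank regimens: the documents contain no rates from which that could be judged. The possibility of reversal is algebraic; every rate and reversal frequency given here is an assumption or depends on one.

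**What to change.** Before unblinding, state in SAP 11.8.2 and 11.9.2 that:

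- the tested endpoint is Clinical Cure at TOC together with absence of signs and symptoms at FU;
- the denominator is all subjects in the analysis population concerned;
- subjects not cured at TOC, and those with a missing TOC or FU result, are non-responders;
- the proportion still clear among TOC cures is reported descriptively, with its denominator and no p-value.

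Record the clarification against the Protocol definition in SAP 12, since a reader could take the Protocol wording as cured-only.

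The cost is SAP wording; no data or procedures change. The reported percentages will be lower than the conditional ones (60% and 43% instead of 75% and 87% in the example). The tested rate will also reflect cure and its maintenance together, which is why the descriptive rate should stay beside it.

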11.3 Discontinuation Criteria

A subject may be discontinued from the study or study drug for any of the following reasons:

- Withdrawal of consent;
- Investigator or sponsor decision that withdrawal is in the subject's best interest;
- Occurrence of an AE that, in the opinion of the investigator, warrants discontinuation of the subject from the study drug;

- Lost to follow up (every attempt should be made to contact the subject)

The reason for a subject’s discontinuation of treatment or withdrawal from the study will be clearly documented in the source documents and on the electronic case report form (eCRF). All TOC procedures should be performed for subjects who discontinue from the study before the TOC visit. All FU visit procedures should be done for subjects who discontinue after the TOC visit but before the FU visit.

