14.10 Rating of Vulvovaginal Signs by the Investigator Using the VSS Scale

The investigator (or qualified designee) will perform vulvovaginal examinations to rate the subject's signs of infection at the Screening, TOC and FU visits, as well as at unscheduled visits. Investigators will assess the signs of infection using the VSS Scale provided in [Section 21.0 \[Appendix B\]](#), a standardized, predefined scale, where each sign of the vagina and/or vulva will be given a numerical rating based on severity, as follows:

- Edema: absent = 0; mild = 1; moderate = 2; severe = 3
- Erythema: absent = 0; mild = 1; moderate = 2; severe = 3
- Excoriation or fissures: absent = 0; mild = 1; moderate = 2; severe = 3

Other findings will be recorded using the most relevant medical term in the abbreviated physical examination page of the eCRF.

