14.11 Rating of Vulvovaginal Symptoms by the Subject Using the VSS Scale

Subjects will be asked to rate their vulvovaginal symptoms at Screening, from Day 1 through the TOC visit (Day 10), at the FU visit and at any unscheduled visit.

Subjects will rate their symptoms of infection using the VSS Scale (see [Appendix B](#)), where each vulvovaginal symptom will be given a numerical rating based on severity, as follows:

- Itching: absent = 0; mild = 1; moderate = 2; severe = 3
- Burning: absent = 0; mild = 1; moderate = 2; severe = 3
- Irritation: absent = 0; mild = 1; moderate = 2; severe = 3

From Day 1 through the TOC visit, subjects will rate their symptoms and record their scores on the VSS Scale included in their subject diaries.

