14.15 Subject Diary Completion

Subjects will complete their diaries from Day 1 through the TOC visit. The subject diaries will include the VSS Scale so that subjects can rate their vulvovaginal symptoms. Subjects will record the date of study medication dosing, daily vulvovaginal symptoms, other medical concerns or complaints and concomitant medications used. Subjects will be instructed to return their subject diaries at the TOC visit (Day 10).

After the TOC visit, subjects will not be required to complete a diary but will be instructed to call the site immediately if they experience new or worsening signs/symptoms or medical concerns/complaints. The site will also determine if any signs/symptoms or other medical concerns/complaints recorded on the diary should be reported as AEs. The information from the subject diary will be included as part of the eCRFs.

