15.0 Study Schedule

Detailed schedules of all study visits and procedures are presented in Schedule of Visits and Procedures (Table 2).

Table 2: Schedule of Visits and Procedures (Study SCY-078-204)

Visit	V1	V2	V3		V4	V5	Unscheduled Visits
	Screening ^a	Baseline ^a	On-site (for PK subset only)	Phone contact (for non-PK subjects)	TOC	Follow-up	
Day (allowable window)	D-1 (-2)	D1	D3	D3 (+3)	D10 (±2)	D25 (+4)	
Study Procedures							
Informed consent	X						
Assignment of Subject ID number	X						
Inclusion/exclusion criteria	X	X					
Medical history and demographics	X						
Abbreviated physical exam	X				X		
Urine pregnancy test ^b	X						If needed
Safety labs ^c	X				X		If needed
Vulvovaginal sample for other pathogens ^d and pH	X						If needed
Vulvovaginal sample for KOH ^e	X				X	X	If needed
Vulvovaginal sample for fungal culture ^e	X				X	X	If needed
Rating of vulvovaginal signs by the investigator	X				X	X	X
Rating of vulvovaginal symptoms by the subject	X	X-----X			X	X	X
Randomization		X					
Study drug and subject diary dispensing		X					
Study drug dosing		X-----X					
Subject diary completion		X-----X					

Visit	V1 Screening ^a	V2 Baseline ^a	V3		V4 TOC	V5 Follow-up	Unscheduled Visits
			On-site (for PK subset only)	Phone contact (for non-PK subjects)			
Day (allowable window)	D-1 (-2)	D1	D3	D3 (+3)	D10 (±2)	D25 (+4)	
Study Procedures							
Treatment compliance evaluation and study drug collection			X ^g	X ^f	X		
Subject diary collection					X		
PK sample collection ^g			X		X		
Vital signs	X				X		If needed
Prior & concomitant medication review	X	X	X	X	X	X	X
AE monitoring	X	X	X	X	X	X	X

Abbreviations: AE=adverse event; D=day; EOT=end of treatment; PK=pharmacokinetic; TOC=test of cure; V=visit

- a. The Screening and Baseline visits may be combined.
- b. Results will be reviewed at Baseline (Day 1) before starting/dispersing study drug .
- c. Hematology and blood chemistry. Laboratory safety testing will be performed by a qualified central laboratory at Screening, TOC visit and at unscheduled visits if needed.
- d. Analysis of samples for other pathogens will be done by a qualified laboratory and will include causative agents for bacterial vaginosis and *Trichomonas vaginalis*. Analysis of samples for other pathogens such as *Chlamydia trachomatis*, *Neisseria gonorrhoeae* or *Herpes simplex* may be performed if suspected.

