At the Baseline visit (which may be combined with the Screening visit), eligible subjects will be randomized in equal allocation (at a 1:1:1:1:1:1 ratio) to one of the following 6 active treatment groups (5 experimental groups and 1 active comparator group):

- Treatment Group 1: oral SCY-078 750 mg QD on Day 1 only
- Treatment Group 2: oral SCY-078 300 mg BID on Day 1 only
- Treatment Group 3: oral SCY-078 450 mg BID on Day 1 only
- Treatment Group 4: oral SCY-078 150 mg BID on Days 1 to 3
- Treatment Group 5: oral SCY-078 300 mg BID on Days 1 to 3
- Treatment Group 6: oral fluconazole 150 mg QD on Day 1 only

Subjects will receive randomized treatment from Day 1 through Day 3. For the purpose of maintaining treatment blinding, all randomized subjects will receive matching SCY-078 placebo

tablets and/or matching fluconazole placebo capsules as needed based on treatment assignment, in a double-dummy fashion. During treatment days, subjects will rate their vulvovaginal symptoms and record dosing details, AEs and concomitant medication use daily on subject diaries. On Day 3, a PK Subset consisting of 10 subjects per treatment group (total of 60 subjects) will visit the site to have PK samples drawn pre-dose (immediately before dosing) and at 2-6 hours' post-dose of either the morning or evening dose. Day 3 will be an on-site visit for PK subjects and a phone contact visit (with a window of +3 days) for non-PK subjects. All subjects (both PK and non-PK subjects) will continue to take their assigned study treatment and rate their symptoms of infection within their subject diaries. Treatment compliance will be reviewed either on site or by phone for all subjects. Study drug may be collected from PK subjects who have completed study drug dosing at the time of this visit.

At the TOC visit (Day 10 [± 2]) vaginal samples will be obtained for local KOH testing and for fungal culture by the central laboratory. In addition, susceptibility testing will be done at the central laboratory for all positive cultures for *Candida* spp. The investigators and the subjects will rate the signs and symptoms of infection, respectively, on the VSS Scale. An abbreviated physical exam, vital sign measurements and safety laboratory tests will also be performed.

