10.4 Analysis Visit Window

Wherever applicable, efficacy and safety endpoints at Visit 1/ Screening, Visit 2/ Baseline, Visit 3/ Day 3, and Visit 5/ FU/ Day 25 will be analyzed according to their nominal visits. Visit 4/ TOC/ Day 10 will be analyzed according to the analysis window of study day 8 to study day 13, inclusive. Unscheduled visits from subjects who attended the TOC visit late will be included if within the analysis window. The bounds may be revised after reviewing blinded data. If more than one evaluation is assigned to this window, the evaluation closed to study day 10 will be used for the analysis. If the two visits are equidistant from the target day, the earlier visit will be used. Unscheduled visit assessments will be displayed in by-subject listings, without being included in the summaries.

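### Read literally, joint resolution of signs and symptoms can be dated only at TOC or FU, so the log-rank test cannot see differences in speed before TOC that leave the shares resolved at those visits unchanged

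*SAP*

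**What the plan says.** - **Event and test.** SAP 11.8.2 gives the endpoint as "defined as time (days) from first dose of study medication to the first resolution of signs and symptoms". Early discontinuations are censored at their last available assessment; nothing is said about completers who never resolve. SAP 11.9.2 plans Kaplan-Meier curves and pairwise log-rank tests against fluconazole.
- **Signs.** Under Protocol 14.10 the investigator rates "signs of infection at the Screening, TOC and FU visits, as well as at unscheduled visits". The row "Rating of vulvovaginal signs by the investigator" in Table 2 (Protocol 15.0) agrees: it has no entry at Baseline or Day 3.
- **Symptoms.** From Day 1 through TOC, Protocol 14.11 says "subjects will rate their symptoms and record their scores on the VSS Scale included in their subject diaries". Protocol 14.15 adds: "The information from the subject diary will be included as part of the eCRFs". No diary is required after TOC.
- **Diary in the SAP.** SAP section 3 says "During treatment days, subjects will rate their vulvovaginal symptoms". It mentions diary ratings again in the Day 3 text and has diaries returned at TOC, but no SAP section names the diary as the source for this endpoint.
- **Visit handling.** SAP 10.4 analyses TOC over study days 8 to 13 and FU by nominal visit. Late TOC visits inside the window count. Otherwise: "Unscheduled visit assessments will be displayed in by-subject listings, without being included in the summaries". The SAP does not say whether this binds the time-to-event analysis.
- **Early withdrawal.** Protocol 11.3 requires that all "TOC procedures should be performed for subjects who discontinue from the study before the TOC visit", so these subjects can have a sign rating at another time.

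**The concern.** The study chooses among one-day and three-day regimens, and this is the only listed efficacy endpoint that could show how fast relief comes. The event needs both components to be absent, but one of them is not looked at between first dose and TOC. A subject whose symptoms clear on Day 3 and another whose symptoms clear on Day 7 get the same kind of event time, the date of the TOC appointment. The comparison then largely repeats the TOC cure comparison. A null log-rank result could be read as no difference in speed when speed before TOC was never measured. The daily symptom scores that could show it are already collected, yet SAP 11.9.1 summarises VSS scores only at Baseline, TOC and FU.

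**Working it through.** The plan states no power, event count or effect size for this endpoint, so there is no figure to reproduce. All timing inputs below are assumptions for illustration.

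**Step 1. When the joint event can be seen after first dose**

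| Component | Scheduled ratings | Study days |
|---|---|---|
| Symptoms | daily diary, then FU | 1 through TOC; 25-29 |
| Signs | TOC, FU | 8-13 (SAP window); 25-29 |
| Both | TOC, FU | 8-13; 25-29 |

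Unscheduled and early-withdrawal visits can add a few other dates.

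**Step 2. Worked example with equal shares at both visits.** Assume 30 per arm. In each arm 18 clear before TOC (all on Day 7 in arm A, all on Day 3 in arm B), 6 more clear on Day 20, and 6 never clear. The log-rank statistic is (O - E)²/V for arm B. At each event time E adds d·n₁/n, and V adds d·(n₁/n)(1 - n₁/n)(n - d)/(n - 1).

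*Dated at visits (Day 10 and Day 25).* E = 36 × 30/60 + 12 × 12/24 = 18 + 6 = 24, and O = 24. The statistic is 0 and p = 1.00.

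*Dated daily.*
- E = 18 × 30/60 + 18 × 12/42 + 12 × 12/24 = 9 + 5.14 + 6 = 20.14, and O = 24.
- V = 3.20 + 2.15 + 1.57 = 6.92.
- The statistic is 3.86²/6.92 = 2.15 and p = 0.14.

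Visit dating removes the four-day gap completely. Daily dating recovers it only in part at this sample size.

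**Step 3. How much the diary could show.** Two arms of 30, with k resolving in each arm and the rest censored at Day 10. Symptom-free days are cycled over the ranges shown.

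| Range of days (faster v slower) | k = 16 | k = 24 | k = 28 |
|---|---|---|---|
| 2-5 v 4-7 | p = 0.41 | 0.03 | 0.0002 |
| 2-7 v 4-9 | 0.53 | 0.12 | 0.007 |
| 3-6 v 4-7 | 0.63 | 0.20 | 0.027 |

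For the first row with k = 28, the slower arm has O = 28, E = 38.60 and V = 7.86, so the statistic is 10.60²/7.86 = 14.3. With identical visit dates and outcomes, the visit-dated p is 1.00 in every cell. The diary result depends heavily on the spread, the gap and the number resolving.

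**Step 4. Simulation with equal shares.** 1,500 trials per scenario, 30 per arm, two-sided 5%. TOC falls on Days 8-12 and FU on Days 25-29. Mean resolution days for those clearing before TOC are 6 v 4, 6 v 3 or 7 v 3 (SD 1.2).

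| Resolved by TOC / FU | Log-rank, visit dates | Log-rank, daily dates |
|---|---|---|
| 50% / 70% | 4-5% | 9-15% |
| 60% / 80% | 5% | 16-26% |
| 70% / 85% | 5-6% | 29-47% |

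The visit-dated test rejects at about its type I error rate.

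**Step 5. Speed that also changes the TOC share.** Exponential times, hazard ratio 2, slower-arm share s by Day 10 of 55, 65 or 75%. The faster-arm share is 1 - (1 - s)², which is 80, 88 or 94%. The 55% is the fluconazole therapeutic cure rate in Protocol 7.1, used only as an anchor. The n = 22 is an assumed mITT size.

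| Analysis | n = 22 per arm | n = 30 per arm |
|---|---|---|
| Joint endpoint, visit dates, log-rank | 31-38% | 40-49% |
| TOC share, chi-square | 39-43% | 51-53% |
| TOC share, Fisher (planned test) | 28-32% | 36-42% |
| Diary symptoms, log-rank | 46-55% | 58-68% |

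These are simulated values, good to a few percentage points. They assume that signs clear with symptoms. The diary row covers symptoms only, so it is not a like-for-like gain.

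**Step 6. Sensitivity to visit timing.** With identical resolution but TOC on Days 8-10 in one arm and Days 10-12 in the other, the visit-dated test rejects in about 20% of trials.

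**The case against.** The strongest objection is that the SAP nowhere says that event times are visit dates. SAP 11.8.2 leaves the date open, the diary enters the eCRF, and a programmer could take the first symptom-free diary day. This stands as a limit on the claim. A reader might infer that the SAP prescribes visit dates; it does not, and visit dating follows only from reading the joint definition against the sign-rating schedule. But the diary holds no signs, so a diary date would not be the event as written, and the SAP needs a sentence either way.

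The illustrations also rest on chosen inputs. This stands too. Step 3 shows the diary p-value moving from 0.0002 to 0.007 with a wider spread alone, and with 16 of 30 resolving no scenario comes near significance. The 20% in step 6 needs a systematic difference in visit dates, which blinding and randomisation make unlikely.

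The weight is limited. The endpoint is secondary, the study is stated not to be powered for formal comparisons, and no document says that this endpoint decides the dose.

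Finally, Protocol 9.2 and 18.7.2 specify time to resolution of signs and symptoms by Kaplan-Meier. Replacing it with a symptoms-only endpoint, or turning first resolution into sustained resolution, would go beyond the defect. That is right, and the fix below adds to the protocol endpoint without displacing it.

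**Conclusion.** The point holds in a limited form. Followed literally, the analysis cannot detect a difference in speed before TOC that leaves the shares resolved at TOC and FU unchanged, apart from what a few early-withdrawal or unscheduled visits add. This follows from the rating schedule and needs no simulation. The missing event-date rule and the missing censoring rule for completers who never resolve are gaps on any reading.

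Two stronger readings are not supported. One is that the endpoint says nothing about speed: when speed also changes the TOC share, it keeps about 40-49% power at 30 per arm under the step 5 assumptions. The other is that diary data would bring a large gain: with equal shares, daily dating gave anywhere from 9% to 47% in step 4, at the low end when few resolve. Nothing here touches the primary endpoint. The change is worth making because it is cheap and the data are already collected.

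**What to change.** Before unblinding, in SAP 11.8.2 and 11.9.2:

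1. Keep the protocol's signs-and-symptoms endpoint. State that its event times are visit dates and whether unscheduled visits count, and censor completers who never resolve at their last assessment.
2. Add, as a supplementary analysis of speed, time to symptom resolution from the daily diary, citing Protocol 14.11 and 14.15 (Day 1 through TOC) as the source. The event is the first diary day with itching, burning and irritation all scored 0. Use Kaplan-Meier and log-rank. Censor subjects not resolved at the last diary or TOC symptom rating. A missing diary day does not count as resolution.
3. Count as unresolved any subject who meets the SAP 11.8.1 clinical failure rule for added treatment.
4. Optionally, as a sensitivity analysis, require that no later non-zero score is recorded through TOC.
5. Record the addition in SAP section 12.

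The cost is SAP wording and one extra diary derivation, with no new data or visits. The downside is that the added analysis covers symptoms only, so it supplements the protocol endpoint and cannot stand in for it.
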